CLINICAL STUDY PROTOCOL

Study Title: An Open-Label Study of the Pharmacokinetics of a Single Dose of Telavancin in Pediatric Subjects Aged 12 months to 17 Years

Study Short Title: Telavancin Pediatric PK Study (Ages > 12 months to 17 Years)

Sponsor Study No.: 0101

ClinicalTrials.gov No.: NCT02013141

Date: 26 August 2019, Amendment 5
31 January 2019, Amendment 4
20 September 2016, Amendment 3, Version 1.0
25 August 2015, Amendment 2
18 April 2014, Amendment 1
04 December 2013, Original Protocol

Test Product: Telavancin

US IND: [REDACTED]

Sponsor: Cumberland Pharmaceuticals Inc.
[name]
[name]

This study will be conducted according to the principles of Good Clinical Practice.

PROTOCOL SYNOPSIS

Study Number and Title: Study 0101: An Open-Label Study of the Pharmacokinetics of a Single Dose of Telavancin in Pediatric Subjects Aged > 12 months to 17 Years

Study Short Title: Telavancin Pediatric PK Study (Ages > 12 months to 17 Years)

Estimated Number of Study Centers and Countries or Regions: At approximately 10 sites in the United States (US)

Background and Rationale:

Telavancin is a rapidly bactericidal, injectable antibiotic with concentration-dependent activity against clinically important Gram-positive pathogens. Telavancin is approved in the US for treatment, in adults, of complicated skin and skin structure infections and hospital-acquired and ventilator-associated bacterial pneumonia (HABP/VABP) caused by susceptible isolates of *Staphylococcus aureus*. This study is designed to evaluate the single-dose pharmacokinetics (PK) of telavancin in pediatric subjects to support development of a dosing algorithm that will deliver exposures similar to those found to be safe and effective in adults.

The most common adverse events, which occurred in $\geq 10\%$ of telavancin-treated patients in Phase 3 studies of complicated skin and skin structure infections (cSSSI), were taste disturbance, nausea, headache, vomiting, foamy urine, and insomnia. In these studies, telavancin was compared in a blinded manner to vancomycin. Serious adverse events were reported in 7% of patients treated with telavancin, and the most common included renal, respiratory, and cardiac events. Treatment discontinuations due to adverse events occurred in 8% of patients treated with telavancin, the most common events being nausea and rash. The incidence of adverse events indicative of renal impairment (increased serum creatinine, renal insufficiency, and renal failure) was 3% of telavancin-treated patients, and serious adverse events indicative of renal impairment occurred in 1% of telavancin-treated patients.

Telavancin has also been evaluated in two Phase 3 trials in adults for hospital-acquired bacterial pneumonia and ventilator-associated bacterial pneumonia, again in a blinded comparison with vancomycin. Serious adverse events were reported in 31% of patients treated with telavancin. Treatment discontinuations due to adverse events occurred in 8% of patients who received telavancin, with the most common events being acute renal failure and QTc interval prolongation. Treatment-emergent adverse events reported in 5% or more of telavancin-treated patients included nausea, vomiting, and acute renal failure. The incidence of adverse events indicative of renal impairment (acute renal failure and increased serum creatinine) was 10% of telavancin-treated patients, and serious adverse events indicative of renal impairment occurred in 2% of telavancin-treated patients.

Telavancin has linear, predictable PK in the adult population. Mean plasma clearance after multiple dosing of 10 mg/kg every 24 hours in adults is 13.1 mL/hr/kg; the mean volume of distribution at steady state is 133 mL/kg, and the mean elimination half-life is 8.1 hours. Approximately 90% of telavancin is bound to plasma proteins, primarily albumin. Telavancin is predominantly eliminated renally, with approximately 60% of the dose excreted unchanged in urine over 48 hours.

PROTOCOL SYNOPSIS (CONTINUED)

Objectives:

Primary:

- To characterize the pharmacokinetics of telavancin after a single dose in pediatric subjects (>12 months to 17 years inclusive) who require systemic antibiotic therapy for the treatment or prevention of a known or suspected bacterial infection

Secondary:

- To assess the safety and tolerability of telavancin after a single dose in pediatric subjects (> 12 months to 17 years inclusive) who require systemic antibiotic therapy for the treatment or prevention of a known or suspected bacterial infection

Study Design: This is a multicenter, open-label, single-dose pharmacokinetic (PK) study. Infants, children, and adolescents will receive a single dose of telavancin infused intravenously (IV) over approximately 60 minutes.

Duration of Study Participation: Up to 9 days

Number of Subjects per Group:

In total, approximately 30 male and female infants, children, and adolescents will be enrolled into the study, as follows:

1. Adolescents (12 to 17 years), N = 8
2. Older Children (6 to 11 years), N = 8
3. Younger Children (2 to 5 years), N = 8
4. Infants >12 and < 24 months, N = 6

Cohorts 1, 2, 3 and 4 will be enrolled in parallel (simultaneously).

Study Population:

Male or female infants, children, and adolescents (> 12 months to 17 years, inclusive) who require systemic antibiotic therapy for the treatment or prevention of a known or suspected bacterial infection.

Inclusion Criteria:

Subjects who meet all of the following criteria will be eligible for study enrollment:

1. Subject is > 12 months to 17 years of age (inclusive)
2. Subject's weight is within the 3rd to 97th percentile (inclusive) for age and sex. Refer to Appendix 1 through Appendix 4.
3. Written informed consent and assent (if appropriate for older age groups) has been obtained per institutional review board (IRB) policy and requirements, consistent with ICH guidelines.
4. Male and female subjects of reproductive potential (i.e., post-pubertal males and post-menarche females) must agree to use a highly effective method of contraception

PROTOCOL SYNOPSIS (CONTINUED)

throughout study period and for 30 days after administration of study drug. A highly effective method of birth control is defined as one that results in a low failure rate (i.e., <1% per year) when used consistently and correctly, such as condom + diaphragm, condom + spermicide, diaphragm + spermicide; or intrauterine device (IUD) with documented failure rate of <1% per year; or oral/injectable/implanted hormonal contraceptives used in combination with an additional double-barrier method; or sexual abstinence.

5. Female subjects who are post menarche are required to have a negative serum pregnancy test before the administration of study drug.
6. Subject requires or recently completed systemic antibiotic therapy for the treatment or prevention of a known or suspected bacterial infection. If completed, the last administered dose of systemic antibiotic must be within 24 hours of enrollment.

Exclusion Criteria:

1. Subject has an estimated creatinine clearance $<50 \text{ mL/min/1.73 m}^2$ (Schwartz equation).
2. Any clinically significant abnormal laboratory value, including hematology, chemistry, or urinalysis that in the judgement of the investigator would make it difficult to assess the pharmacokinetic profile and safety of a single dose of telavancin or would compromise the safety of the subject.
3. Any clinically significant medical history, abnormal physical examination finding, or vital sign measurement, including evidence of hemodynamic instability or significant collections of fluid outside normal vascular and tissue compartments (e.g., large pleural effusions, ascites), that in the judgement of the investigator would make it difficult to assess the pharmacokinetic profile or safety of a single dose of telavancin or would compromise the safety of the subject.
4. Subject has clinically relevant cardiac abnormality, in the opinion of the investigator, such as:
 - a. A mean QTcF $>440 \text{ msec}$, congenital long QT syndrome, second or third degree heart block at rest.
 - b. Hemodynamically significant heart disease, eg, hemodynamically unstable congenital heart defect, uncompensated heart failure, uncorrected abnormal calcium, hyperkalemia, or any other unstable cardiac condition.
 - c. An arrhythmic heart condition requiring medical therapy
5. Subject is receiving an anticoagulant AND requires specific coagulation testing (Prothrombin Time/International Normalized Ratio, Activated Partial Thromboplastin Time, Activated Clotting Time, or Coagulation Based Factor X Activity Assay) within 24 hours of receiving the telavancin dose. NOTE: Although telavancin does not interfere with coagulation, it interferes with some assays used to monitor coagulation.
6. Subjects who are receiving concomitant vancomycin treatment should not be assessed for vancomycin serum concentrations within 24 hours of receiving the Telavancin dose. NOTE: Telavancin might interfere with some Vancomycin therapeutic drug monitoring

PROTOCOL SYNOPSIS (CONTINUED)

assays. Caution should be exercised when interpreting vancomycin drug monitoring levels in the presence of telavancin.

7. Subject has a history of allergies or hypersensitivities to glycopeptide antibiotics (e.g., vancomycin), telavancin, or the formulation excipients.
8. Subject requires, or is anticipated to require, concomitant [within 24 hours before or 24 hours following the single dose of study medication (telavancin)] administration of agents that in the clinical judgment of the investigator increase the risk of torsade de pointes.
9. Subject is considered unlikely to comply with the study procedures.
10. Subject was treated with an investigational drug within 30 days or five half-lives, whichever is longer, before study entry.
11. Subject has any other condition that, in the opinion of an investigator, would confound or interfere with evaluation of safety of the investigational drug, or prevent compliance with the study protocol.

Test Product, Dose, and Route of Administration; Regimen; Duration of Treatment:

Telavancin 10 mg/kg will be administered as a single IV infusion over approximately 60 minutes to children in the 3 older age groups: Adolescents (12 to 17 years), Older Children (6 to 11 years), Younger Children (2 to 5 years). The appropriateness of the dose(s) used in children > 12 months to < 24 months will be assessed during interim PK analyses of telavancin concentration-time data, including PK exposure estimates. The pediatric exposure estimates will be compared to historical data in adults to facilitate adjustment of the dose for the youngest age group. Pharmacokinetic results completed to date indicate that telavancin exposure is consistent with initial modeling projections; exposure was observed to decrease with decreasing body weight.

Reference Therapy, Dose, and Route of Administration; Regimen; Duration of Treatment: Not applicable

Study Evaluations

Safety Assessments:

Subject safety will be monitored during the study using standard measures, including physical examinations, vital signs, 12-lead ECGs, clinical laboratory assessments, urinalysis, concomitant medication usage, and adverse event reporting.

Pharmacokinetic Assessments:

Blood samples for PK assessment will be taken as follows: 1.0 hour (± 5 min), 1.5 hours (± 5 min), 2 hours (± 5 min), 6 hours (± 30 min), 12 hours (± 30 min) and 24 hours (± 30 minutes) after the beginning of the infusion. The timing of PK sampling may be optimized after the completion of the older age groups (Cohorts 1-3) to assure that the minimum numbers of samples are collected in the youngest age group > 12 months to < 24 months. Plasma exposures that will be compared to adult exposures are the primary assessment for this study.

PROTOCOL SYNOPSIS (CONTINUED)

Plasma will be assayed for the determination of telavancin and the primary metabolite (AMI-11352).

Statistical Methods:

Sample Size:

The standard regulatory requirement for sample size in pediatric studies is to prospectively power to target a 95% confidence interval within 60% and 140% of the geometric mean estimates of clearance (CL_p) and volume of distribution (V_{dss}) in each pediatric age subgroup with at least 80% power.

Approximately 30 male and female infants, children, and adolescents will be enrolled into the study.

The subjects entered will be stratified by age:

- Adolescents (12 to 17 years), N= 8
- Older Children (6 to 11 years), N = 8
- Younger Children (2 to 5 years), N = 8
- Infants > 12 and < 24 months, N = 6

Sample size for each pediatric age subgroup was determined on the basis of the variability in telavancin PK parameters from adult data.

Study Endpoints:

The primary study analysis variables are the telavancin PK parameters: C_{max} , T_{max} , AUC_{0-t} , AUC_{0-inf} , and $t_{1/2}$ (as appropriate) derived from plasma concentration-time data.

The secondary endpoints are safety variables (see Safety Assessments above).

Analysis:

Noncompartmental and/or population PK methods will be used for determination of plasma PK parameters. All PK parameters will be presented by individual listings and summary statistics according to age stratification, including mean, geometric mean, median, standard deviation, 95% confidence interval, and coefficients of variation, minimum, maximum and number of subjects. Further analyses of the potential relationship between PK parameters and subject age may be performed. Plasma concentration data may also be utilized for development of a pediatric population PK model.

Safety information gathered will be tabulated and descriptively summarized.

SCHEDULE OF STUDY PROCEDURES

Table 1: Schedule of Assessments

Procedure	Screening (Up to 48 Hours Before Dosing)	Day 1	Day 2	Follow Up (Day 8 ± 1 Day) ^h
Assent if appropriate and Informed Consent	X			
Review Inclusion/Exclusion Criteria	X	X		
Medication and Medical History	X			
Weight and Height/Length	X			
Vital Signs ^a	X	X	X	
ECG (12-lead) ^b	X	X		
Physical Examination	X			
Serum Pregnancy Test ^c	X			
Hematology, Serum Chemistry, Urinalysis ^d	X ^d		X ^d	
Telavancin Drug Dosing		X		
Plasma PK Sampling ^e		X	X	
Concomitant Medications	X	X	X	X ^g
Adverse Events	X	X	X	X ^g

Abbreviations: ECG, electrocardiogram; PK, pharmacokinetic

- a Vital signs (Heart rate [HR], blood pressure [BP], respiratory rate [RR] and body temperature) will be measured following dosing as outlined in Table 2. HR and BP will be measured after a subject has rested for at least 5 minutes in the seated or supine position.
- b ECGs (12-lead) will be recorded after a subject has rested for at least 10 minutes in the supine position. If the screening ECG is collected less than 24 hours before study drug dosing, the ECG prior to dosing may be omitted. The ECG on Day 1 may be collected between 1.5 and 2.5 hours (±10 minutes) after commencement of the telavancin infusion.
- c Pregnancy tests will be performed on female patients who are post menarche.
- d If standard clinical laboratory tests have been performed within the protocol-specified windows for laboratory testing at screening and Day 2, the results may be used to avoid excessive blood draws. Only hematology and chemistry laboratory testing is required on Day 2.

SCHEDULE OF STUDY PROCEDURES (CONTINUED)

- e Blood samples for plasma PK analysis of telavancin will be collected as outlined in Table 2.

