3.3 Selection of Dose and Duration of Treatment

Infants, children, and adolescents will receive a single intravenous (IV) telavancin dose infused over approximately 60 minutes. The initial starting dose of 10 mg/kg for the first eight subjects is the approved dose for treatment of complicated skin and skin structure infections (cSSSI) and treatment of hospital-acquired and ventilator-associated bacterial pneumonia (HABP/VABP) caused by susceptible isolates of *Staphylococcus aureus* in adult patients with creatinine clearance >50 mL/min.

Dose selection for the current study was based upon the current approved dose in adults (10 mg/kg), preclinical data, and simulations of the anticipated plasma exposure to telavancin in pediatric patients based on the adult telavancin population PK model and allometric scaling of telavancin clearance and volume of distribution to pediatric patients.

The effect of telavancin was evaluated in juvenile rats in a repeated-dose toxicity study. Based on these results, the effects of telavancin on juvenile animals did not differ

substantively from the effects in adults. A summary of the juvenile toxicology data may be found in the current version of the telavancin IB.

Clearance and volume of distribution were scaled allometrically from the adult population PK model across the pediatric age and weight range on the basis of an assumed allometric exponent of 0.75 (clearance) and 1.0 (volume of distribution), respectively.

Pediatric PK simulations were conducted utilizing a uniform distribution of body weights between 9.6 kg (average weight of a 1-year old child, based on WHO growth standards) and 70 kg. The distribution of creatinine clearance (CrCL) values was taken from the observed distribution of subjects in the adult population PK model and constrained to ≥ 50 mL/min in accordance with the study protocol. The age of each subject in the simulations was estimated by utilizing the average weight vs. age from the Centers of Disease Control and Prevention (CDC) growth charts for children in the United States {3}. Additionally, the values of CrCL for subjects 1 to 2 years of age were reduced by 15% to reflect dependence of renal function on size, organ maturation, and body composition {4}.

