PK simulations for a pediatric dataset of 1500 subjects ($n = 200$ simulations per subject) and dose of 10 mg/kg were conducted using the population PK model and categorized by the age stratification that is defined in the protocol (Table 3). The mean and standard deviation of exposures (area under the curve [AUC]) in the pediatric population are anticipated to be lower than the 864 ± 285 $\mu\text{g}\cdot\text{hr}/\text{mL}$ observed at day 4 in the Phase 3 adult population (Studies 0015, 0017, 0018, and 0019) after a dose of 10 mg/kg (18 to 65 years of age, $n = 393$).

The selected dose level (10 mg/kg) is therefore anticipated to maintain plasma exposure to telavancin at comparable or lower levels than previously observed in the adult population. The results of this study will be utilized to design dosing algorithms in pediatric patients intended to maintain comparable exposures to the approved dose in adults. The appropriateness of the 10 mg/kg dose will be evaluated after enrollment of Cohorts 1-4.

Table 3: Exposures to Telavancin Based on a Population Pharmacokinetic Model in Pediatric (Predicted) and Adult (Actual) Subjects

Age Range	Estimated AUC ₀₋₂₄ (µg·hr/mL) (Mean ± SD)
Adult*	864 ± 285*
12 – 17 years	628 ± 214
6 – 11 years	537 ± 185
2 – 5 years	457 ± 160
1 – 2 years	433 ± 155

* Observed exposure on day 4 from Phase 3 clinical data (n = 393)

Note: Simulations based on a total of 300,000 simulated subjects at a telavancin dose of 10 mg/kg

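### Does Table 3's adult AUC of 864 sit on a different scale from its simulated pediatric rows, so that the comparison with adult exposure is unsound?

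*Combined protocol and SAP*

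**What the plan says.** The Synopsis (Pharmacokinetic Assessments) states: "Plasma exposures that will be compared to adult exposures are the primary assessment for this study". Section 3.1 carries this out by generating exposure estimates for each subject from the refined population PK model and setting them against historical adult observations. It names no adult value.

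Section 3.3 describes the pre-study simulation behind Table 3. Clearance and volume were scaled from the adult population PK model "on the basis of an assumed allometric exponent of 0.75 (clearance) and 1.0 (volume of distribution), respectively". Weights were drawn from "a uniform distribution of body weights between 9.6 kg (average weight of a 1-year old child, based on WHO growth standards) and 70 kg". The creatinine clearance (CrCL) distribution "was taken from the observed distribution of subjects in the adult population PK model", limited to at least 50 mL/min, and "the values of CrCL for subjects 1 to 2 years of age were reduced by 15" per cent. Table 3 then lists mean AUC0-24 of 628 ± 214 (12–17 years), 537 ± 185 (6–11), 457 ± 160 (2–5) and 433 ± 155 (1–2). The adult row is 864 ± 285, footnoted as observed on day 4 in 393 Phase 3 patients. The table title marks the pediatric values as predicted and the adult value as actual. Section 3.3 does not say whether the pediatric AUC0-24 is first-dose or steady-state, and gives no model-predicted adult value.

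Section 3.3 concludes that pediatric exposure should be comparable to or lower than in adults, and that the results will be used to "design dosing algorithms in pediatric patients intended to maintain comparable exposures to the approved dose in adults". Section 8.5.6 refits the model after each set of eight subjects.

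**The concern.** With clearance proportional to weight to the power 0.75 and a fixed mg/kg dose, AUC varies only as weight to the power 0.25. Going from a 70 kg adult to a 9.6 kg infant then lowers AUC by about 39%. Table 3 shows a drop of 50% (433 against 864). Even adolescents, many of them near adult weight, are 27% lower (628/864 = 0.73). On a weight-only reading, the 2–5 and 1–2 year rows are lower than any simulated child could produce from 864.

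If the adult row and the pediatric rows are on different scales, part of what Section 3.3 presents as lower pediatric exposure is not an effect of body size. The synopsis and Section 3.1 describe results to date as consistent with the initial modeling, and that agreement would not validate the link to adults. The fear is that a later dosing algorithm would carry an unexplained offset, and that Section 8.5.6 contains no step, such as simulating adults with the same model, that would expose it.

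**Working it through.** **Inputs from the protocol.** Table 3 AUCs; exponents 0.75 and 1.0 and the 9.6 kg minimum (Section 3.3); adult clearance 13.1 mL/hr/kg, half-life 8.1 h and about 60% urinary excretion (Section 1.1); 10 mg/kg over 1 h.

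**Assumptions, not in the protocol.** Adult mean weight 70 to 100 kg. Uniform weights within bands of 40–70, 20–40, 12.5–20 and 9.6–12.5 kg for the four age groups. A one-compartment shortcut for the share of AUC reached by 24 h, with half-life scaled as weight^0.25.

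**What can be reproduced.** 1500 subjects × 200 simulations = 300,000, matching "Simulations based on a total of 300,000 simulated subjects at a telavancin dose of 10 mg/kg". The AUCs themselves cannot be reproduced, because the model's parameters and CrCL effect are not given.

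**Step 1, the floor from 864.** AUC = 864 × (9.6/W_adult)^0.25.
- 70 kg adult: 525.8; 100 kg adult: 480.9.
- As first-dose AUC0-24: 525.8 × 0.963 = 506; 480.9 × 0.973 = 468.

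Both 457 and 433 are lower. To reach 433 at 9.6 kg, the adult weight would have to be 9.6 × (864/433)^4 = 152 kg.

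**Step 2, all rows scaled from 864.**

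| Age (years) | Table 3 | From 864, 70 kg | Ratio | From 864, 100 kg | Ratio |
|---|---|---|---|---|---|
| 12–17 | 628 | 812 | 0.77 | 742 | 0.85 |
| 6–11 | 537 | 697 | 0.77 | 637 | 0.84 |
| 2–5 | 457 | 599 | 0.76 | 548 | 0.83 |
| 1–2 | 433 | 544 | 0.80 | 498 | 0.87 |

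The rows are 13 to 24% below values scaled from 864. If they are first-dose AUC0-24, the ratios are 0.81–0.88 (70 kg) and 0.87–0.94 (100 kg), that is 6 to 19% below.

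**Step 3, the protocol's other adult anchor.** Dose/CL = 10 mg/kg ÷ 13.1 mL/hr/kg = 763 µg·hr/mL. Read as first-dose AUC0-24:

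| Age (years) | Table 3 | From 763, 70 kg | Ratio | From 763, 90 kg | Ratio |
|---|---|---|---|---|---|
| 12–17 | 628 | 632 | 0.99 | 604 | 1.04 |
| 6–11 | 537 | 564 | 0.95 | 537 | 1.00 |
| 2–5 | 457 | 500 | 0.91 | 474 | 0.96 |
| 1–2 | 433 | 461 | 0.94 | 437 | 0.99 |

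Table 3 lies within −9% to +4% of these values. The floor at 9.6 kg is now 447 (70 kg) or 423 (90 kg), so 457 is not excluded, nor is 433 for the heavier adult.

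**Step 4, limits of that agreement.** Dose divided by mean clearance understates mean AUC. With a log-scale SD of 0.284 (Section 8.2), the factor is exp(0.284²) = 1.084, giving 828. Dividing the Step 3 ratios by 1.084 gives 0.84–0.92 (70 kg) and 0.89–0.96 (90 kg). The 15% CrCL cut at 1–2 years lowers clearance by 0.6 × 15% = 9% (60% renal share) to 15% (clearance proportional to CrCL). This takes the infant ratio in the Step 3 table to between 0.939 × 0.85 = 0.80 and 0.992 × 0.91 = 0.90, ignoring its small effect on the share reached by 24 h.

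**Step 5, do the pediatric rows form one line?** With adolescents at 50–60 kg, weight^0.25 scaling puts the infant row at (433/628)^4 × 50 to 60 = 11.3–13.6 kg, which is plausible. Allowing for the CrCL cut multiplies this by 0.91^4 = 0.69 or 0.85^4 = 0.52, giving 5.9–9.3 kg, below the simulated minimum. So the infant row also leaves the weight-only line, which points to the shortcut rather than to the adult row alone.

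**The case for a change.** The strongest case for acting is that the shortfall from 864 is systematic: all four ratios lie in 0.76–0.80 at 70 kg, first-dose truncation does not remove it, and the CrCL cut widens it for infants. The protocol carries two adult levels, 864 and 763, without reconciling them. Explaining the gap through CrCL alone, on a 60% renal share, would need CrCL some 23 to 56% higher in the simulated children than in the Phase 3 adults, and nothing states that. A simulated adult row would cost almost nothing.

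Much of this stands as description. The weight-only arithmetic is right, the AUC basis of the pediatric column is unlabelled, and the adult link is unexplained. What does not stand is the step to an impossible value or a flawed comparison. The simulation starts from the model's own clearance, and the reference list describes that model as built on healthy subjects and infected patients, a different mix from the Phase 3 group. Table 3 openly sets predicted beside actual. The protocol never names 864 as the formal benchmark.

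Nor does the consequence follow. Section 3.3 uses Table 3 for one conclusion, that pediatric exposure should be comparable or lower. Values scaled from 864 (about 544 to 812 at 70 kg) support it equally well. The reviews under Sections 3.1 and 8.5.6 use exposures fitted to the children's own concentrations, with covariate relations open to revision. If the aim is to match exposure seen in adults, the total gap is what matters, whatever its split between size and population.

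**Conclusion.** No change to the plan is needed. By weight alone, Table 3's pediatric rows are 13 to 24% below values scaled from 864, or 6 to 19% if they are first-dose AUC0-24. From the protocol's own clearance (763) they are within −9% to +4% for 70 to 90 kg adults, a fit that weakens once mean AUC and the infant CrCL cut are treated strictly. These ranges rest on assumed adult weights, assumed weight bands and a one-compartment shortcut. They show that the cause cannot be determined from the documents, not that 457 or 433 is wrong.

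A model-predicted adult row would help interpret a pre-study rationale table. It would not alter any estimate, confidence interval or observed adult target. The missing details, namely the AUC basis of Table 3 and the exact form of the adult comparison in Section 8.5.6, are ones that pharmacokinetic analysts fill sensibly. Section 1.1 describes linear kinetics, under which single-dose AUC0-inf, already an endpoint, is the natural counterpart of a steady-state 24-hour AUC. Geometric means and 95% confidence intervals by age group are already planned.
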